10.2 Sample Size, Accrual Time and Study Duration

Power and Sample Size Considerations. Sample size for this study was estimated using a 2-group test of non-inferiority of proportions, with the 2-year invasive breast cancer rate in the surgery group assumed to be 0.10 based on published studies.^{61,62} The non-inferiority margin assumed was 0.05. Based on a 1-sided un-pooled z-test, with alpha=0.05, a sample size of n=446 per group will have 80% power⁶⁴ to detect the specified non-inferiority margin. The proportion of patients who decline the arm to which they are specifically randomized can diminish the estimate of treatment difference, and could also widen the confidence bounds, but the analytical approaches proposed here aim to diminish the impact on bias of the treatment difference. With a 3-year duration of accrual and 2 additional years of follow-up, we anticipate approximately 148 total events.

Analysis of Primary Outcome (See below for outcomes definitions). This trial was designed anticipating non-acceptance of arm allocation, and the proportion of patients that do not accept their arm allocation can lead to bias in estimates of treatment differences. Thus, we plan to complete several analyses of the primary outcome, reporting the primary intent to treat (ITT) analysis as well as sensitivity analyses that are intended to reduce the bias in estimation of treatment difference in this setting.

We assume that a clinically acceptable difference in 2-year invasive cancer diagnosis rate in order to conclude non-inferiority is 5%. Cumulative incidence curves will be used to estimate the invasive cancer diagnosis rates over time, and at the 2-year point, the difference in rates will be estimated and a 1-sided upper confidence bound of (AM-GCC) will be computed, using methods described by Austin.⁶⁵ We will conclude that AM is not inferior to Surgery if the upper confidence bound on the risk difference at 2 years is less than 5%.

ITT Analysis. The ITT analysis of 2-year invasive cancer diagnosis rate will be conducted using all patients, as randomized, and will be completed using Kaplan-Meier estimates, stratified by group, combined with the Greenwood's confidence interval. The difference in invasive cancer risks will be computed from the Cox model with treatment at 2 years, with a 1-sided 95% confidence interval of the difference (AM-GCC) computed.

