Sensitivity analyses. Several sensitivity analyses are planned, including a per protocol analysis, as treated analysis, an instrumental variable analysis, as well as a principal stratification analysis.^{68,69} The sensitivity analysis will account for loss of follow-up, rejection of randomization allocation and withdrawals, and pre-randomization factors influencing rejection of randomization, described in further detail below.

Intent-to-treat (ITT) analysis is typically the standard in reporting results of clinical trials. However, in the presence of rejection of randomization allocation (here defined as selecting surgery when randomized to AM, and choosing AM when randomized to surgery), ITT results can be biased;⁶⁶⁻⁶⁸ similarly per protocol (PP) and as-treated (AT) analyses could yield biased estimates, especially since these analyses may no longer maintain balance achieved by randomization. Cuzick et al⁶⁶ outline an approach to measure treatment effect among compliers, which follows the randomization (e.g. ITT), but assures that the estimates are not diluted by allocation changes. Thus, studies using this approach are similarly powered to ITT analysis, but provide appropriately wider confidence limits, which will be critical in a non-inferiority study. Principal stratification approaches can improve upon the width of confidence intervals and can

allow for covariate adjustment to aid in this improvement. Additionally, the covariates can aid in identifying subgroups with differential clinical response or treatment preference.

We recognize the potential to lose patients to follow-up; yet, we consider approaches that could still provide some level of information for all patients who were randomized. Dunn et al⁶⁷ describe instrumental variable methods with inverse probability weighting for missing data and latent class models as two approaches to deal with loss to follow-up. Each approach makes assumptions, most of which are feasible for this trial, but we will report the assumptions as well as the comparative analyses in the literature and disseminate findings. We will also assess sensitivity to departures from these assumptions through simulation studies.

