At interim time-points as the study is enrolling, we plan to assess the level of withdrawal from the study completely, as well as the level of rejection of allocation or later changes in treatment (can only occur in Active Monitoring arm). We will utilize these levels to carry out simulation studies, but with parameters based upon ranges around our observations during the trial enrollment in order to assess our ability to maintain unbiased results of the treatment differences, particularly in the context of a non-inferiority setting. We will also implement sensitivity to the assumptions made in these simulations, including missing data mechanism (MD-5). If all of the approaches are generally equal in reducing bias, we will report on the approach that maintains alpha level and appropriate non-inferiority conclusion as our primary focus, but will also report the other approaches as comparators. The simulation results will be reported as evidence supporting conclusions, when applicable.

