10.7 Survival Follow up

Any study participant can choose to withdraw from the study at any time for any reason, including no specified reason. Patients in the surgery arm cannot opt for the AM arm after surgery, but in the event that a patient withdraws from the study, the date of withdrawal and reason for withdrawal will be recorded. The patient will be censored in time-to-event analyses at the date of withdrawal from the study

Patients in the AM arm may choose to either withdraw from the study or opt to proceed with surgery at any time. In the event that a patient in the AM arm opts to proceed with surgery in the absence of invasive progression, the date of withdrawal and reason for withdrawal will be recorded. As for the surgery arm, in the event that a patient withdraws from the study, the patient will be censored at the date of withdrawal from the study.

Patients in the AM arm with progression to invasive breast cancer are required by the study protocol to proceed with surgery for their invasive breast cancer. Patients who have invasive breast progression and do not wish to have surgery will continue to remain in follow up with their invasive cancer event recorded, at the time of invasive breast progression for the primary analysis. For further exploratory analyses, the lack of surgery for these patients will be recorded.

For patients who choose to no longer be followed per the protocol schedule, the patient can choose to enter the Survival Follow-up Phase. Survival data, ongoing adjuvant therapies and subsequent disease progression data will be collected during this phase of the study every 12 months for 10 years from registration. Telephone contact is acceptable as well as medical record review.

Follow-up will be discontinued early due to:

- Patient Death
- Patient Withdrawal of consent for all follow-up
- Patient deemed lost to follow-up

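### Section 10.2 does not say that the choice of a primary focus leaves the ITT analysis in place, and Section 10.7 can be read as censoring monitoring-arm patients who elect surgery

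*Combined protocol and SAP*

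**What the plan says.** **Choice of analysis.** Section 10.2 (Analysis of Primary Outcome) commits to "reporting the primary intent to treat (ITT) analysis as well as sensitivity analyses". Non-inferiority is concluded if the upper bound on the 2-year risk difference is below 5%. The ITT analysis "will be conducted using all patients, as randomized".

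Under Sensitivity analyses, the same section plans to assess, while the trial enrols, "the level of withdrawal from the study completely, as well as the level of rejection of allocation or later changes in treatment", and to run simulations based on those levels. It continues: "If all of the approaches are generally equal in reducing bias", then "we will report on the approach that maintains alpha level and appropriate non-inferiority conclusion as our primary focus". The other methods are to be reported as comparators.

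**Elective surgery in the AM arm.** Section 10.7 says that AM patients "may choose to either withdraw from the study or opt to proceed with surgery at any time". For those who choose surgery without invasive progression, it records a date of, and reason for, withdrawal. The next sentence censors patients who withdraw from the study at their withdrawal date.

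Section 5.2.2.1 treats the same patients as having declined their arm, offers them continued follow-up, and refers to Section 11.2. Section 6.1.2 calls this a change in management. Table 3 in Section 10.2, which sets out which occurrences are events, ignored or censored, has no row for elective surgery or for withdrawal.

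**The concern.** **Choice of analysis.** Three features leave the headline analysis less firmly fixed than it should be. ITT is not excluded from the set of approaches, and the preceding text lists it with per-protocol and as-treated among the analyses that can be biased. One criterion for selection is an appropriate non-inferiority conclusion, which can be read as depending on the result. No date or event closes the choice. In an open-label trial that expects patients to decline their allocation, readers need to see that the analysis carrying the claim was settled before outcomes by arm were known.

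**Elective surgery.** The only date that Section 10.7 attaches to these patients is called a withdrawal date, and it sits directly before the censoring rule. A programmer who follows that wording would censor them out of an analysis defined on all patients as randomized. Table 3 does not settle the matter, and Section 11.2 (Regulatory and Ethical Compliance) contains no rule. Censoring would change the AM 2-year rate, in a direction that depends on how the date is set.

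**Working it through.** **The plan's own figure.** Inputs from Section 10.2: 10% in each arm, margin 5 points, one-sided alpha 0.05, 80% power, unpooled test.

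n = (1.645 + 0.842)² × (2 × 0.10 × 0.90) / 0.05² = 445.1, rounded up to 446 per group, as stated.

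With the planned 1,080 patients (540 per arm), power is 86%. At 10% risk, non-inferiority then requires an observed difference below 0.05 − 1.645 × √(0.18/540) = 0.0200, or about 2.0 points. A shift of one point is half of that room.

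**(a) Choosing among analyses.** The documents give no crossover rate, so crossover is assumed. Trials of 540 per arm were simulated with a true ITT difference of 5 points and one-sided 95% bounds. In the instrumental-variable (IV) analysis the bound is the ITT bound divided by the difference in uptake.

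Chance of declaring non-inferiority, with risk set by assigned arm (15% against 10%) and random crossover in each arm:

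| Crossover | ITT | Any of ITT, per-protocol, IV | As-treated alone |
|---|---|---|---|
| 2% | 5.0% | 5.6% | 6.1% |
| 5% | 5.0% | 6.0% | 8.4% |
| 10% | 5.1% | 6.5% | 12.8% |

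- With risk set by treatment received, ITT gives 5.1-5.3% and any of the three gives 5.2-5.6%.
- The excess over ITT is therefore about 0 to 1.5 points, and only if the choice is made after results. It is zero if the choice is locked beforehand.
- As-treated is left out of the choice because it fails the plan's own alpha criterion in the first model.
- IV adds nothing. Its bound is the ITT bound divided by a number below 1, so it cannot fall under 5% when the ITT bound does not. The excess comes from per-protocol alone.
- Principal stratification was not modelled.

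**(b) Censoring elective surgery.** Let x be the share of AM patients electing early surgery, r the 2-year risk in the rest, and u the share with invasive cancer at that surgery. Section 1.6 gives 0-20% for upstaging at excision, which is used for u; x and r are assumptions. Assume first that leavers have no later event.

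- True AM rate: (1 − x)r + xu.
- Censored before the operation, so the event is lost: the estimate is r and the shift is x(r − u).
- Event at the operation counted, other leavers censored: the estimate is 1 − (1 − xu)(1 − r) and the shift is xr(1 − u).

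Example with x = 0.10, r = 0.06, u = 0.20: event lost, 0.10 × (0.06 − 0.20) = −1.4 points; event counted, 0.10 × 0.06 × 0.80 = +0.5 points.

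Shift in points as u goes from 0 to 20%:

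| x | r | Event lost | Event counted, others censored |
|---|---|---|---|
| 5% | 6% | +0.3 to −0.7 | +0.3 to +0.2 |
| 5% | 10% | +0.5 to −0.5 | +0.5 to +0.4 |
| 10% | 6% | +0.6 to −1.4 | +0.6 to +0.5 |
| 10% | 10% | +1.0 to −1.0 | +1.0 to +0.8 |
| 20% | 6% | +1.2 to −2.8 | +1.2 to +1.0 |
| 20% | 10% | +2.0 to −2.0 | +2.0 to +1.6 |

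If leavers without invasion at surgery have later risk v, the last column becomes x(1 − u)(r − v). It is positive only while v is below r.

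Simulated operating characteristics (540 per arm, surgery at months 0.5-3, Kaplan-Meier with Greenwood variance):

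- Event lost, true 15% against 10%, u = 10%, 15%, 20%: false non-inferiority 3.1%, 5.7%, 9.7% at x = 10%, and 1.8%, 6.3%, 17.3% at x = 20%. Without censoring it is 5.0-5.4%.
- Event counted, true 10% against 10%, u = 10%: power 79%, 70%, 48% at x = 5%, 10%, 20%, against 86% without censoring.

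**The case against.** **On (a).** A reader might infer that Section 10.2 lets the sponsor replace ITT with whichever method gives non-inferiority. The documents do not support that. ITT is named primary with its own decision rule. The sentence sits under Sensitivity analyses, and the section uses the word approaches mainly for methods meant to reduce bias from non-acceptance. Maintaining alpha is something simulations can judge and a single result cannot. Those simulations use crossover and withdrawal levels, not outcome differences, and every method is to be reported. What stands is that ITT is not expressly outside the choice, one criterion is worded as a conclusion, and there is no lock point.

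**On (b).** A reader might infer that the plan censors AM patients who elect surgery. The better reading is that it does not:

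- Section 10.7 opens by presenting withdrawal and surgery as alternatives. Its closing list of reasons for ending follow-up early (death, withdrawal of consent for all follow-up, loss to follow-up) omits elective surgery.
- Section 10.2 defines rejection of allocation ("here defined as selecting surgery when randomized to AM, and choosing AM when randomized to surgery") and separates it from complete withdrawal.
- Sections 5.2.2.1 and 6.1.2 agree, as does an ITT set of all patients as randomized.
- Some patients will decline the offer of continued follow-up, and a withdrawal date is needed for them. Ipsilateral invasive cancer is already an event in Table 3, however it is found.

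So the figures in (b) describe a coding error, not the plan as best read. The 17.3% needs both 20% crossover and 20% upstaging, twice the 10% in Section 2.1; at 10% upstaging, false non-inferiority falls below 5%. Nor does censoring always make AM look worse when the event is counted. What stands is that the literal wording of Section 10.7 can be coded as censoring, and neither Table 3 nor Section 11.2 corrects it.

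**Conclusion.** Both points hold as defects of wording that bear on the primary analysis.

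(a) is a gap in pre-specification, not a demonstrated alpha error. Its possible size is about 0 to 1.5 points of one-sided alpha, on assumed crossover of 2-10% and a choice made after results.

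(b) is an internal inconsistency. Taken literally, Section 10.7 censors patients whom the rest of the plan keeps in follow-up. At an assumed 10% crossover with 6-10% risk in the remaining patients and 0-20% upstaging, the AM rate would shift by about +1.0 to −1.4 points if the event is lost, and by about +0.5 to +1.0 if it is counted and the other leavers have no later event. That matters against a 5-point margin where only about 2 points of observed difference are allowed.

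The reference to Section 11.2 is wrong in any case. Several other cross-references run one section too high (Sections 6 and 9.1 cite 7.1.3, Table 1 cites 9.1.1, Section 10.6 cites 7.1.1), which suggests 10.2. That section also speaks of "The proportion of patients who decline the arm to which they are specifically randomized". Section 10.7 is possible too, so the target is an inference.

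**What to change.** **Section 10.2.** State that the non-inferiority conclusion rests on the ITT analysis alone, that all other methods are sensitivity analyses whatever they show, and that any simulation-based choice among them is documented before outcomes by arm are examined.

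**Sections 10.7, 5.2.2.1 and 6.1.2.** Reconcile them by stating that, for the ITT analysis:

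- surgery without invasive progression in the AM arm is a change of treatment and not a withdrawal;
- these patients stay uncensored while followed;
- invasive cancer found at that or later surgery is an AM event;
- censoring applies only at withdrawal of consent for all follow-up, at loss to follow-up, or at death from other causes as Table 3 provides.

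**Table 3.** Add two rows: elective surgery without invasive progression, Ignore (invasive cancer in the specimen follows the existing first row); withdrawal of consent for all follow-up, Censor.

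**Cross-reference.** The sponsor should correct the Section 5.2.2.1 reference to 11.2, confirming whether 10.2 or 10.7 is meant.

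**Cost.** Wording only; sample size and alpha do not change. The sponsor gives up later freedom over the headline analysis, and the AM rate may be slightly less favourable than if events at elective surgery were dropped.

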3.1 Inclusion Criteria

- Diagnosis of unilateral, bilateral, unifocal, multifocal or multicentric DCIS without invasive breast cancer (date of diagnosis defined as the date of the first pathology report that diagnosed the patient with DCIS) **OR:** atypia verging on DCIS **OR:** DCIS + LCIS (mix and/or separate locations in the same breast)
- A patient who has also had a lumpectomy or partial mastectomy with margins positive for DCIS (i.e. <2mm/ink on tumor) as part of their treatment for a current DCIS diagnosis is eligible (post-excision mammogram required at enrollment to establish a new baseline)
- No previous DCIS or invasive breast cancer in ipsilateral breast 5 years prior to current DCIS diagnosis
- 40 years of age or older at time of DCIS diagnosis
- ECOG performance status 0 or 1
- No contraindication for surgery
- Baseline imaging (must include dimensions):
 - unilateral DCIS: contralateral normal mammogram \leq 6 months of registration and ipsilateral breast imaging \leq 120 days of registration (must include ipsilateral mammogram; can also include ultrasound or breast MRI)
 - bilateral DCIS: bilateral breast imaging \leq 120 days of registration (must include bilateral mammogram; can also include ultrasound or breast MRI)
 - DCIS s/p lumpectomy: post excision mammogram on side of excision \leq 60 days of registration
- Pathologic criteria:
 - All grade I DCIS (irrespective of necrosis/comedonecrosis)
 - All grade II DCIS (irrespective of necrosis/comedonecrosis)
 - Absence of invasion or microinvasion
 - Diagnosis of DCIS confirmed on core needle biopsy, vacuum-assisted biopsy or surgery \leq 120 days of registration

- ER(+) and/or PR(+) by IHC ($\geq 10\%$ staining or Allred score ≥ 4) unless atypia verging on DCIS in which case biomarker criterion does not apply
 - HER2 0, 1+, or 2+ by IHC if HER2 testing is performed
- Histology slides reviewed and agreement between **two** clinical pathologists (not required to be at same institution) that pathology fulfils COMET eligibility criteria. In cases of disagreement between the two pathology reviews about whether the case fulfils the eligibility criteria, a third pathology review will be required.
- At least two sites of biopsy for those cases where individual mammographic extent of calcifications exceeds 4 cm, with second biopsy benign or both sites fulfilling pathology eligibility criteria (ER/PR testing required for second biopsy)
- Amenable to follow up examinations

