5.1.2.2 Radiotherapy

The recommendation for post-surgical radiotherapy should be decided following surgery and prescribed according to standard local protocols. The use of post-surgical radiotherapy is not mandated within the trial. However, data on the use of radiotherapy will be collected.

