Participant subgroups and planned subgroup analyses. We hypothesize that both clinical outcomes and PRO measures may be dependent upon treatment arm and patient characteristics. Pre-specified subgroups for assessment of heterogeneity of treatment effect will include (1) **endocrine therapy** (yes/no as well as duration of therapy); (2) **choice of surgery** (lumpectomy or mastectomy); (3) **receipt of radiation** (yes/no); (4) **mode of monitoring** (q 6 month MMG versus additional imaging, i.e. ultrasound or MRI); (5) **race** (African-American women compared to white women; other minorities will also be assessed for HTE, but precision is likely to be low); (6) **menopausal status** (pre-or post-menopausal, as reported by the patient); (7) **baseline risk of invasive breast cancer** based on modified Gail Score; (8) **burden of comorbidities** at diagnosis which will impact the magnitude of clinical benefit derived from surgery for DCIS. These subgroup analyses will be completed using methods described by Austin⁶⁵ to estimate the average treatment effect (ATE) and the average treatment effect for the treated (ATT), using adjusted Cox models. The ATE would answer the question about how outcomes would change if a policy was instituted that all patients eligible for either therapy were only offered the “experimental therapy”, which here is Active Monitoring. We also consider the use of time-dependent methods for endocrine therapy and receipt of radiation therapy, using the Austin approaches as well, with time-dependent covariates in the Cox models.

Definitions of outcomes

Subsequent local breast events (SLBE) events are coded as one of the following types:

- **iINV:** Ipsilateral invasive in-breast cancer (includes chest wall recurrence)
- **iCIS:** Ipsilateral in situ in-breast cancer
- **cINV:** Contralateral invasive in-breast cancer (includes chest wall recurrence)
- **cCIS:** Contralateral in situ in-breast event cancer
- **iLX:** Ipsilateral lymph node cancer
- **cLX:** Contralateral lymph node cancer

Distant breast cancer metastasis (DistMet) is the only non-SLBE breast event considered

Ipsilateral invasive breast event is defined as first occurrence of either of the following:

- (i) *ipsilateral invasive breast cancer*,
- (ii) *ipsilateral lymph node cancer in the absence* of a preceding ipsilateral invasive breast cancer event,

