Planned subgroup analyses (NCDB Special Study). The large DCIS registry developed through collaboration with the National Cancer Database (NCDB) will allow for the continued collection of long-term outcomes for patients as well as for the comparison of primary and secondary outcomes (when measurable in NCDB) for **AM versus surgery** amongst those patients who are randomized and accept their arm allocation versus those patients who are randomized but do not accept their arm allocation versus patients not registered or randomized to COMET, but who generally meet our broad inclusion criteria for the trial. Patients will be identified from all study sites during the time interval of COMET accrual. These analyses will be from predominantly non-randomized patients, so we plan to utilize observational study approaches for analyses. We will use full regression models (logistic or Cox model, dependent upon outcome measure) to control for potential confounders, including pathology, age, race, academic versus community setting, among others. As in other analyses, we will utilize inverse-probability weighting to handle missing data.⁷⁰

Analyses of long-term outcomes. Analyses of long-term outcomes will follow the approaches outlined above, modifying the year of rate calculations, accordingly. PRO data will utilize longitudinal linear mixed models over time, following appropriate scoring and transformation, if needed.

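### Four of the eight pre-specified effect-heterogeneity subgroups are set by care after randomisation, and radiation and endocrine therapy can be consequences of the endpoint

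*Combined protocol and SAP*

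**What the plan says.** Section 10.2, under participant subgroups, opens its list with "Pre-specified subgroups for assessment of heterogeneity of treatment effect will include". Items 1 to 3 are endocrine therapy, surgery type and radiation: "yes/no as well as duration of therapy); (2) choice of surgery (lumpectomy or mastectomy); (3) receipt of radiation (yes/no". Item 4 is mode of monitoring, contrasting six-monthly mammography with additional imaging. Items 5 to 8 are race, menopausal status, modified Gail score and comorbidity at diagnosis.

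One method is given for all eight: "to estimate the average treatment effect (ATE) and the average treatment effect for the treated (ATT), using adjusted Cox models". The section adds: "We also consider the use of time-dependent methods for endocrine therapy and receipt of radiation therapy". It does not separate items 1 to 4 from items 5 to 8, does not name the population for each factor, and calls none of them non-randomised.

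Other sections fix the timing. Section 5.1.2.2 states: "The recommendation for post-surgical radiotherapy should be decided following surgery and prescribed according to standard local protocols". Section 5.1.2.3 likewise places surgery-arm endocrine therapy after surgery. Section 2.1 puts upstaging found at surgery at 10% in that arm.

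**The concern.** A subgroup analysis of a randomised comparison keeps its protection when the subgroup is fixed before allocation. Four of these eight are not.

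The clearest problem is radiation and endocrine therapy. In the surgery arm both decisions follow the pathology that reveals most of the expected primary events. Membership of the radiation or endocrine stratum can therefore result from the endpoint. Adjustment for baseline covariates does not remove that.

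For surgery type, radiation and mode of monitoring there is a second difficulty: each belongs to the planned care of one arm only, so a stratum in one arm has no valid counterpart in the other.

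What is at stake is interpretation. A difference in the AM effect by radiation or endocrine therapy would be reported as a pre-specified finding with a causal estimand attached, and could be read as evidence on which patients suit AM. Section 10.2 also carries its approach forward to the long-term outcomes.

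**Working it through.** **The plan's own figure.** For the primary test, with 10% in each arm, a 5-point margin, one-sided alpha 0.05 and 80% power: n = (1.645 + 0.842)² × 2 × 0.10 × 0.90 / 0.05² ≈ 445.2, rounded up to 446 per group as stated. The point here does not depend on it.

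**When each factor is settled.**

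| Factor | When and where it is settled | Source |
|---|---|---|
| Endocrine therapy, duration | Chosen after allocation in both arms; after surgery in the surgery arm; use in the 6 months before registration is excluded | 1.4, 3.2, 5.1.2.3, 5.2.2.2 |
| Surgery type | Chosen by patients allocated to surgery | 1.4 |
| Radiation | After surgery; scheduled for the surgery arm only | 5.1.2.2, Table 1 footnote 6 |
| Mode of monitoring | Six-monthly ipsilateral mammography required in the AM arm only; extra imaging arises in follow-up | 6.1.1 |
| Race, menopausal status, Gail score, comorbidity | Baseline | 10.2 |

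Four of eight follow randomisation.

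**Counterpart in the other arm.** Surgery and radiation are not allocated care under AM. An AM patient may nevertheless have had surgery or radiation through excision before entry (section 3.1: "A patient who has also had a lumpectomy or partial mastectomy with margins positive for DCIS"), invasive progression or declining the arm (5.2.2.1), or a contralateral event (5.3.3). None of these makes a group comparable with surgery-arm patients who had lumpectomy or radiation, and section 10.2 does not say how AM patients would be placed.

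**Size, illustrated for radiation.** From the documents: 2-year risk r = 0.10 in the surgery arm (sections 2.1 and 10.2). Assumed: the same risk under AM, so no true effect; a fixed yes/no split; the whole AM arm as comparator; all surgery-arm events known before the radiation decision; radiation share p1 in upstaged patients and p0 = 0.50 in the others.

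- Risk if irradiated = r·p1 / [r·p1 + (1 − r)·p0]
- Risk if not = r·(1 − p1) / [r·(1 − p1) + (1 − r)·(1 − p0)]

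At 80%/50%: 0.08/0.53 = 15.1% and 0.02/0.47 = 4.3%.

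| p1 / p0 | Surgery risk, radiation | Surgery risk, none | AM − surgery, radiation | AM − surgery, none |
|---|---|---|---|---|
| 80% / 50% | 15.1% | 4.3% | -5.1 | +5.7 |
| 60% / 50% | 11.8% | 8.2% | -1.8 | +1.8 |
| 50% / 50% | 10.0% | 10.0% | 0 | 0 |
| 40% / 50% | 8.2% | 11.8% | +1.8 | -1.8 |
| 30% / 50% | 6.3% | 13.5% | +3.8 | -3.5 |

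If only half the events are known at the decision, replace p1 by 0.5·p1 + 0.5·p0. At 80%/50% this is 0.65, giving 0.065/0.515 = 12.6% and 0.035/0.485 = 7.2%, hence -2.6 and +2.8 points. At 60%/50% the result is -0.9 and +0.9. The distortion is about halved.

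**The case against.** The plan is not blind to selection. Section 1.4 warns of selection and treatment biases within arms and promises covariate adjustment. In a time-dependent Cox model, treatment given after an event cannot count towards that event, so the mechanism illustrated above would disappear there. Both points are fair. But section 10.2 leaves time-dependent methods under consideration, mentions them for two of the four factors, and neither safeguard restores a randomised contrast. The plan is more careful elsewhere in the same section: of per-protocol and as-treated analyses it says "especially since these analyses may no longer maintain balance achieved by randomization", and of the registry comparison "These analyses will be from predominantly non-randomized patients, so we plan to utilize observational study approaches for analyses".

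A reader might infer that all four factors are explicitly planned as AM-versus-surgery contrasts. The text does not go that far. Mode of monitoring reads as a comparison within the AM arm, and section 10.5 restricts surgery type to women allocated to surgery, though only for patient-reported outcomes. For these two the defect is mainly an unnamed population.

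A reader might also infer that the direction of the false signal is known, or that it must reverse according to how AM patients are classified. Neither is supported. Section 5.1.2.2 leaves radiation to local protocols, and nothing says whether upstaged patients receive it more or less often. The table therefore runs both ways, and any reversal depends on an assumption that the documents do not supply.

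**Conclusion.** The concern holds. Four of the eight subgroups are post-randomisation, and section 10.2 attaches ATE and ATT estimates to them without a non-randomised label or a named population. Endocrine therapy and radiation are the serious cases because, in the surgery arm, the endpoint can determine the stratum.

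With no true effect, and under the stated assumptions, the false difference for radiation runs from -5.1/+5.7 through zero to +3.8/-3.5 points. For scale, the primary margin is 5 points. These sizes rest on assumed radiation shares, a fixed split and the whole AM arm as comparator; the conclusion about the design of the subgroups does not.

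It would be wrong to infer that the main result is compromised. The primary intention-to-treat comparison uses all patients as randomised, no decision rule is attached to these subgroups, and the sample size stands. This should be corrected in the plan, but it does not threaten the primary conclusion.

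**What to change.** In the subgroup paragraph of section 10.2:

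- Restrict effect-heterogeneity analyses (ATE/ATT) to baseline factors: race, menopausal status, baseline risk score and comorbidity, plus the prior-excision subset already promised in section 10.3. Adding the three stratification factors is optional.
- Report endocrine therapy, surgery type, radiation and imaging mode within arm only. Name the population for each, label the results non-randomised, and make no ATE or ATT claim.
- Commit to time-dependent handling of endocrine therapy and radiation. For that analysis, start surgery-arm follow-up after surgery and exclude upstaging events. At 2 years, report receipt descriptively.

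The change is to SAP wording and needs no new data. The price is that fewer factors are reported as effect modifiers.
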